APPENDIX D: IMPUTATION OF PARTIAL MISSING SUBSEQUENT ANTICANCER THERAPY START DATE

Subsequent anticancer therapy start date will be imputed if both month and year are present and only day is missing.

- If the year of the subsequent anticancer therapy start date is the same as the year of the EOT date,
 - If the month of subsequent anticancer therapy start date is the same as the month of the EOT date, then the subsequent anticancer therapy start date will be imputed as the EOT date.
 - If the month of the subsequent anticancer therapy start date is later than the month of the EOT date, then the subsequent anticancer therapy start date will be imputed as the first day of the month.
 - If the month of the subsequent anticancer therapy start date is earlier than the month of the EOT date, then the subsequent anticancer therapy start date will be imputed as the last day of the month.
- If the year of the subsequent anticancer therapy start date is later than the year of the EOT date, then the subsequent anticancer therapy start date will be imputed as the first day of the month.

If the EOT date is missing, then the EOT date will be the end-of-study (EOS) date or 30 days after the last dose of any study drug, whichever is earlier.

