6.3.4 Day 15 (+2 days)

- Predose (to occur on day of dosing unless noted below)
 - Vital signs
 - CBC with differential (may be collected the day prior to dosing)
 - Serum chemistry panel (may be collected the day prior to dosing)
 - Blood samples for PK assessments (within 24 hours prior to dose; Cycles 1 and 2)
 - Blood samples for biomarker assessments (within 24 hours prior to dose; Cycle 1)

- Enfortumab vedotin administration. At least 1 week must elapse between doses of enfortumab vedotin.
- Postdose
 - Blood samples for PK assessments (Cycles 1 and 2)

6.3.5 Day 17

- Blood samples for PK assessments (-24/+48 hours; Cycles 1 and 2)

6.3.6 Day 22

- Blood samples for PK assessments (Cycles 1 and 2 [\pm 48 hours])
- CT scan with contrast (if contraindicated, see [Appendix F](#)) of the chest, abdomen, pelvis and any other region of known or suspected disease (every 8 weeks [\pm 1 week] from Cycle 1 Day 1 during treatment, with repeat scans 4 weeks [$+1$ week] after first documentation of response). Brain and/or bone scans should also be repeated at this timepoint if metastases were identified at baseline, or if metastasis is suspected. After 1 year on study the frequency of scans will be reduced to every 12 weeks (\pm 1 week). Following confirmation scans, response assessments should continue with the previous scan schedule (i.e., the schedule should not be adjusted). If there is a dose delay due to toxicity, the schedule for response assessments will not be adjusted and will continue to be timed from Cycle 1 Day 1 during treatment. Tumor imaging should also be performed whenever disease progression is suspected.

6.4 End of Treatment Visit (30 to 37 days after last dose of study drug)

EOT visits should occur 30 to 37 days after the last dose of study drug unless delayed due to an AE. However, EOT evaluations must be performed before initiation of a new therapy for cancer, with the exception of the slit lamp examination. If EOT evaluations are completed before 30 days after the last study treatment, the patient will be contacted 30 to 37 days following the last treatment to assess for adverse events.

- QLQ-C30
- EQ-5D
- Slit lamp examination (for patients who experience corneal adverse events during the study). Performed \geq 4 weeks from last dose.
- Pregnancy test (either serum or urine) for females of childbearing potential
- Physical exam (including weight)
- Vital signs
- CBC with differential
- Serum chemistry panel

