6.5 Handling of Dropouts and Missing Data

Missing data will not be imputed unless otherwise specified.

For time-to-event endpoints (e.g., duration of response, PFS, and OS), subjects who have no specified event will be censored as specified for each respective endpoint in Section 7.5.

Subjects who do not have at least two (initial response and confirmation scan) post-baseline response assessments will be counted as non-responders for the analysis of primary endpoint.

Missing AE dates will be imputed for the purpose of calculating duration of events and treatment-emergent status (see [Appendix A](#) for imputation details and [Appendix B](#) for treatment-emergent definition).

Missing prior therapy dates will be imputed for the purpose of calculating the time from prior therapy to first dose of study drug (see [Appendix C](#) for details).

Missing subsequent anticancer therapy start date will be imputed for the purpose of deriving the time-to-event endpoints as applicable (see [Appendix D](#) for details).

Unless otherwise specified, if the numeric value of a laboratory test is not available because it is below the lower limit of quantification (LLOQ), the result will be analyzed as equal to the LLOQ when a numeric value is required (e.g., calculating the mean) and be listed as “< LLOQ” in the listings.

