7.5.3 Duration of Response

DOF is defined as the time from the date of first documented response (CR or PR that is subsequently confirmed) to the date of first documented PD per RECIST v1.1 or death due to any cause, whichever comes first.

DOF will be censored as described below:

- Subjects who do not have PD and are still on study at the time of an analysis will be censored at the date of the last adequate response assessment documenting absence of PD
- Subjects who have started a new anticancer treatment (with the exception of palliative radiotherapy on a non-target lesion that is not progressing) prior to documentation of PD will be censored at the date of the last adequate response assessment prior to start of new treatment
- Subjects who discontinue from the study prior to documentation of PD will be censored at the date of the last adequate response assessment documenting absence of PD.

DOF per IRF will only be calculated for subjects achieving a confirmed CR or PR per IRF. DOF will be analyzed using Kaplan-Meier methodology and Kaplan-Meier plots will be provided. The median DOF and its two-sided 95% CI will be calculated. In addition, the DOF at 6 and 12 months will be summarized.

Sensitivity Analysis

The following sensitivity analysis will be performed for the DOF per IRF:

1. A sensitivity analysis to censor subjects who progressed or died after an extended loss to follow up (i.e., ≥ 2 consecutive missed response assessments) at the date of the last adequate response assessment prior to the missed visits.

DOF per investigator will be analyzed in the same way as the DOF per IRF.

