7.5.5 Progression-free Survival (PFS)

PFS is defined as the time from start of study treatment to first documentation of PD per RECIST v1.1 or death due to any cause, whichever comes first.

The same censoring rules as outlined in Section 7.5.3 for DOR will be applied to PFS. In addition, subjects who are not known to have died and do not have any post-baseline response assessment will be censored at the date of first dose.

PFS per IRF will be analyzed using Kaplan-Meier methodology and Kaplan-Meier plots will be provided. The median PFS and its two-sided 95% CI will be calculated. In addition, the 6- and 12-month PFS rates will be summarized.

Sensitivity Analysis

The following sensitivity analysis will be performed for the PFS per IRF:

1. A sensitivity analysis to censor subjects who progressed or died after an extended loss to follow up (i.e., ≥ 2 consecutive missed response assessments) at the date of the last adequate response assessment prior to the missed visits.

PFS per investigator will be analyzed in the same way as the PFS per IRF.

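### SAP Appendix D imputes a missing start day for subsequent therapy without checking the PD date, so a PD documented after the EOT date can become a censoring in DOR and PFS

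*SAP*

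**What the plan says.** SAP 6.5 gives the purpose of the imputation: "Missing subsequent anticancer therapy start date will be imputed for the purpose of deriving the time-to-event endpoints as applicable". Appendix D then applies when month and year are known and only the day is missing. Its branches are:

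- therapy in the same month as EOT: "then the subsequent anticancer therapy start date will be imputed as the EOT date";
- therapy in a later month of the same year, or in a later year: "then the subsequent anticancer therapy start date will be imputed as the first day of the month";
- therapy in an earlier month of the same year: "then the subsequent anticancer therapy start date will be imputed as the last day of the month".

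If EOT itself is missing, "the EOT date will be the end-of-study (EOS) date or 30 days after the last dose of any study drug", whichever is earlier. No branch mentions PD or a scan date.

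The imputed date feeds the DOR rule in SAP 7.5.3. A subject who starts new therapy "prior to documentation of PD will be censored at the date of the last adequate response assessment prior to start of new treatment". SAP 7.5.5 carries this over: "The same censoring rules as outlined in Section 7.5.3 for DOR will be applied to PFS".

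On timing, Protocol 6.4 states: "EOT visits should occur 30 to 37 days after the last dose of study drug unless delayed due to an AE". The same section calls for a CT at EOT unless one was done in the preceding 4 weeks. Protocol 7.2 and SAP 4 keep scans going for patients who stop treatment for reasons other than PD. A PD dated after EOT is therefore a planned situation.

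**The concern.** The 7.5.3 rule depends on the order of two dates, PD and new therapy. Appendix D fixes one of them without looking at the other, and for therapy in or after the EOT month it picks an early date. A patient whose PD was seen on a scan, and who then started another therapy, can be recorded as having started it first. The PD drops out and follow-up is cut back to a scan before the imputed start.

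DOR is what is mainly at stake. Protocol 3.2 relies on durability to give the ORR its meaning, and DOR is estimated in responders only, so single events carry weight. PFS is affected by the same mechanism.

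**Working it through.** The plan states no figure for this step, so there is nothing to reproduce. The check is of date logic, followed by a rough size.

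**1. Worked dates.** Scan without PD on 14 January, PD on 11 March (8 weeks later), therapy truly started 25 March, day not recorded.

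| EOT date | Appendix D start | Result under 7.5.3 |
|---|---|---|
| 10 January | 1 March | censored 14 January |
| 10 December, prior year | 1 March | censored 14 January |
| 4 March | 4 March | censored 14 January |
| 20 March | 20 March | PD kept as event |

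The third row assumes no adequate scan between 14 January and 4 March, although a CT would normally be due at that EOT visit.

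**2. When a PD is lost.** Let PD fall on day D of a month with L days, with EOT before PD and therapy g days after PD.

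- If therapy falls in a later month than PD, the imputed date is the 1st of that later month, so PD is kept.
- If therapy falls in the PD month, the imputed date is the 1st or the EOT date. Both precede PD, unless PD is on the 1st.

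So PD is lost when D ≥ 2 and D + g ≤ L, which is L − g − 1 dates per month (zero if negative). The EOT-to-PD lag drops out. Over a 365-day year:

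- g = 7: (365 − 12×8)/365 = 269/365 = 73.7%
- g = 14: (365 − 12×15)/365 = 185/365 = 50.7%
- g = 21: (365 − 12×22)/365 = 101/365 = 27.7%
- g = 28: (7×2 + 4×1)/365 = 18/365 = 4.9%
- g = 35: 0%

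A full enumeration gives the same shares. It covered PD on each day of a year, therapy 1 to 60 days after PD, and EOT from 120 days before to 40 days after PD. With EOT before PD, 602,400 of 2,628,000 combinations (22.9%) lose the PD. With EOT on or after PD, 0 of 887,240 do. A further 10,660 combinations have a therapy year earlier than the EOT year, for which Appendix D has no rule; they are left out.

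**3. Events lost.** The illustrative 30% ORR in 100 patients (SAP 6.2) gives 30 responders. The remaining inputs are assumptions: 10% to 30% of responders have EOT before a documented PD and then start therapy; 5% to 20% of start days are missing; the gap is 21 to 7 days.

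- Low: 30 × 0.10 × 0.05 × 0.277 = 0.04
- High: 30 × 0.30 × 0.20 × 0.737 = 1.33

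**4. Direction.** As a rough guide, take exponential DOR with all 30 responders progressing and each lost PD censored 8 weeks (56/30.4375 = 1.84 months) earlier. An assumed true median of 8 months is then reported as 8.0 to 8.3. That is not the SAP's Kaplan-Meier estimator, which can move the other way. PDs at 5, 5.5, 6, 6.5 and 7 months have median 6. If the 6.5-month PD is censored at 4.66, four remain at risk, survival is 0.75 after 5 and 0.50 after 5.5, and the median becomes 5.5 (5.75 by the midpoint convention).

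**The case against.** **The situation is uncommon, and the shares in step 2 are conditional on it.** This stands. Therapy information is collected at repeated contacts (Protocol 6.7) and data queries are raised in the eCRF (Protocol 8.2), so many missing days can be recovered. The assumed frequencies in step 3 have no source in the documents.

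**A reader might infer that most PDs found soon after dosing stops are exposed.** The documents do not support that. With a CT due at EOT unless one was done in the previous 4 weeks, PD arising soon after the last dose should largely be found at or before EOT, where nothing is lost. The exposed patients are mainly those whose PD appears at scans after the EOT visit.

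**A reader might infer that the bias always favours the drug.** It does not. The example in step 4 shows a Kaplan-Meier median falling. The earlier-month branch also imputes the last day of the month, which can retain a PD that should have been censored.

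**A reader might infer that the primary ORR is at risk**, because SAP 6.4.2 ignores responses after subsequent therapy starts. SAP 6.5 limits this imputation to time-to-event endpoints; if that limit is kept, the primary ORR analysis is untouched.

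**An early imputed start is a defensible conservative choice, and bounding it by PD creates the reverse error.** This stands in part. With EOT 45 days before PD and true starts 3, 7 or 14 days before PD, the bound counts 73.7% of combinations as PD events, against 0% under Appendix D. However, scheduled scans stop once new therapy begins (Protocol 7.2), so a PD documented in that month will usually have come first. Appendix C already bounds imputed dates by known ones.

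**Conclusion.** The point holds and is minor. Appendix D can reverse the order of an observed PD and a later therapy start, and nothing else in the SAP prevents it: the sensitivity analyses in 7.5.3 and 7.5.5 address missed assessments only. Loss requires three things together: EOT before PD, a missing start day, and therapy later in the same calendar month as a PD that is not on the 1st. The shares in step 2 follow from the rule alone once the gap is assumed. The loss of about 0.04 to 1.3 DOR events per cohort rests on the assumptions in step 3. The usual effect is a longer or unchanged DOR or PFS median, with occasional shortening.

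**What to change.** Add to SAP Appendix D: the missing day is queried first; if it stays missing and PD is documented in the same month and year as the therapy start, the imputed start is the later of the Appendix D date and the PD date. Use the IRF PD date for IRF analyses and the investigator PD date for investigator analyses. Report DOR and PFS under the present Appendix D imputation as a sensitivity analysis. In the enumeration above, this bound reduces the 602,400 lost PDs to 0.

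The cost is a short addition to the appendix, the matching code and one extra run of DOR and PFS, with no new data collection beyond the query. Two downsides should be stated. A patient who truly started therapy shortly before PD in that month would count as an event, and one patient may carry different imputed dates in the IRF and investigator analyses. If the SAP is already final, Protocol 9.3 provides for describing and justifying the change in the clinical study report.
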